6.8.1.2 Dose modifications for hematologic toxicity

Patients who have IPs held for hematologic toxicities should have blood counts and differentials checked at least weekly until recovery; these data should be recorded in eCRF as extra laboratory examinations. If counts do not improve to CTCAE Grade 1 or better despite drug cessation for 3 weeks, patients should be referred to a hematologist for further assessment. A bone marrow analysis should be considered per hematology assessment.

For AEs that are unrelated to the study drug, study drug may be withheld for up to 3 weeks at the discretion of the treating Investigator.

Management of anemia

Anemia is a common adverse drug reaction related to olaparib. Cediranib is not reported to increase the risk of anemia. Management of anemia is in accordance with Table 10:

Table 10 Management of anaemia

	Olaparib dose	Cediranib dose
Hb <10 but \geq 8 g/dL	
Give appropriate supportive treatment and investigate causality.
 
Investigator judgement to continue olaparib or interrupt dose for a maximum of 3 weeks.
 
If repeat Hb <10 but \geq8 g/dL, dose interrupt until Hb \geq10 g/dL for maximum of 3 weeks and upon recovery dose reduce to 150 mg bd as a first step and to 100 mg bd as a second step
	No change
Hb < 8 g/dL	
Give appropriate supportive treatment and investigate causality.
 
Interrupt olaparib until improved to Hb \geq10 g/dL.
 
Upon recovery dose reduce olaparib to 150 mg bd
	No change

Abbreviations: bd twice daily; Hb hemoglobin

Common treatable causes of anemia (eg, iron, vitamin B12 or folate deficiencies and hypothyroidism) should be investigated and appropriately managed. In some cases, management of anemia may require blood transfusions. Any subsequently required dose interruptions, related to development of anemia, or coexistent with newly developed neutropenia, and/or thrombocytopenia, will require olaparib dose reductions to 150 mg twice daily as a first step and to 100 mg twice daily as a second step.

If Hb drops to < 8 g/dL despite the dose reduction or more than one blood transfusion is required to recover Hb levels with no alternative explanation for the anemia, olaparib should be permanently discontinued.

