6.8 Management of IP related toxicities

The dose levels and the general approach to dose modification of the cediranib and olaparib component of the combination therapy are shown in Table 7 and Table 8, respectively. Specific dose modification information for some AEs are provided in Section 6.8.3 and Section 6.8.4. Please refer to the current IBs for emerging safety data for cediranib and olaparib: CCI

AEs should be treated with the appropriate maximum supportive care, and dose reductions should be clearly documented in the eCRF.

Table 7 Dose modification cediranib

Dose Level	Cediranib tablets
Initial dose	30 mg daily
Dose reduction 1	20 mg daily
Dose reduction 2	15 mg daily

Table 8 Dose modification of olaparib

Dose Level	Olaparib tablets
Initial dose	200 mg twice daily
Dose reduction 1	150 mg twice daily
Dose reduction 2	100 mg twice daily

At the discretion of the investigator, the study drugs may be held or dose modified independently if the observed toxicity is attributed to only one of the drugs, while the patient continues to receive the drug not associated with the observed toxicity. The time a given drug is held should not exceed 3 weeks. Once dose of study drug(s) have been reduced, no dose re-escalation is permitted.

If treatment has to discontinue due to toxicity, both IPs (cediranib and olaparib) should be discontinued at the same time; patients are not allowed to remain in the study if they are taking either cediranib or olaparib as monotherapy. However, in rare circumstances, patients experiencing ongoing clinical benefit but who develop one of the toxicities listed below related to one of the IPs that prevents them to continue to take this IP, may be allowed to continue on the unrelated drug if in the opinion of the treating investigator the risk benefit remains favorable and only after discussion with the AstraZeneca Study Physician and the Principal Investigator.

AEs requiring cediranib to be discontinued:

- GI perforation
- Arterial Thromboembolic Event
- PRES
- Severe hemorrhage
- Severe persistent hypertension despite maximal anti-hypertensive treatment

AEs requiring olaparib to be discontinued:

- Bone marrow findings consistent with MDS/ AML
- Severe persistent anemia
- Pneumonitis

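### For a patient already at olaparib 150 mg bd whose Hb falls below 8 g/dL, two rules in Protocol Section 6.8.1.2 overlap (next step down, or permanent stop), and the Table 10 row for that event is incomplete

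*Protocol*

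**What the plan says.** All the olaparib instructions for anemia stand in Protocol Section 6.8.1.2, under the general dose rules of Section 6.8.

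- **Table 10, row for Hb below 8 g/dL.** Interrupt olaparib until Hb is back to at least 10 g/dL, then "Upon recovery dose reduce olaparib to 150 mg bd". The row has no condition on first occurrence or current dose, and no second step. The milder row (Hb from 8 to below 10 g/dL) ties the reduction to a repeat event and gives two steps: "upon recovery dose reduce to 150 mg bd as a first step and to 100 mg bd as a second step".
- **Paragraph after Table 10.** "Any subsequently required dose interruptions, related to development of anemia, or coexistent with newly developed neutropenia, and/or thrombocytopenia, will require olaparib dose reductions", first to 150 mg and then to 100 mg twice daily. No lower Hb limit is given.
- **Last paragraph on anemia.** "If Hb drops to < 8 g/dL despite the dose reduction or more than one blood transfusion is required to recover Hb levels", followed by "with no alternative explanation for the anemia, olaparib should be permanently discontinued".
- **Section 6.8.** Table 8 sets the olaparib levels at 200, 150 and 100 mg bd, and the text adds: "Once dose of study drug(s) have been reduced, no dose re-escalation is permitted".

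Olaparib can reach 150 mg bd for reasons other than anemia: neutropenia or thrombocytopenia (Section 6.8.1, Table 9), non-hematologic toxicity (Section 6.8.2, Table 11) or moderate renal impairment (Section 6.8.4.4).

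**The concern.** A site treating a patient at 150 mg bd with Hb below 8 g/dL finds two written rules whose terms she meets, and they lead to different actions. The table row that should be the quick reference names a dose she is already taking. The protocol describes anemia as a common olaparib reaction, so the event is foreseeable, and the synopsis plans about 40 sites for about 60 patients. Different sites could act differently on the same event.

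The first stake is patient safety. The second is analysis. A permanent olaparib stop is a TDT event, because TDT uses the earliest IP discontinuation date when the two drugs stop at different times (Protocol Section 8.4.2; SAP Section 3.2.2). It also enters the counts of AEs leading to discontinuation of either IP (SAP Section 4.2.9), relative dose intensity (SAP Section 3.3.2) and exposure to the combination (SAP Section 4.2.6). In a single-arm study there is no control group against which such handling differences would balance out.

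**Working it through.** The plan gives no figure to reproduce; the check is a comparison of texts. Take an Hb below 8 g/dL with no other cause found, and apply each statement by the olaparib dose at onset.

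| Dose at onset | Table 10 row, read literally | Paragraph after Table 10 | Last paragraph (Hb trigger) |
|---|---|---|---|
| 200 mg bd | 150 mg bd | first step, 150 mg bd | not met, no reduction yet |
| 150 mg bd | 150 mg bd, no reduction | second step, 100 mg bd | permanent stop |
| 100 mg bd | 150 mg bd, an increase | no step left | permanent stop |

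**At 200 mg bd** the row and the paragraph agree.

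**At 150 mg bd** two explicit rules apply. The step-down paragraph covers any later anemia-related interruption, however low the Hb, and "will require olaparib dose reductions to 150 mg twice daily as a first step and to 100 mg twice daily as a second step". The last paragraph covers Hb below 8 g/dL after a reduction and stops olaparib. The row adds nothing usable.

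**At 100 mg bd** the literal row conflicts with the ban on re-escalation in Section 6.8. Only the stop rule can be carried out.

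The outcome at 150 mg bd turns on three points the text leaves open.

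1. *Which step.* If the reduction referred to in the stop rule is the first step, she stops. If it means that both steps have been used, she goes to 100 mg bd.
2. *Which reason.* A patient at 150 mg bd for renal impairment may have her first anemia event there. Nothing says whether that earlier reduction counts.
3. *Reach of the condition.* The proviso about no other explanation follows the transfusion trigger. It may qualify both triggers or only that one. If only that one, an Hb below 8 g/dL after reduction leads to a stop even when another cause is found.

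**Size.** One patient handled one way and not the other changes the discontinuation proportion by 1/60 = 0.0167, about 1.7 percentage points. The documents give no rate for Hb below 8 g/dL on a reduced dose. If 3% to 10% of 60 patients had such an event (an assumption), that is 0.03 × 60 = 1.8 to 0.10 × 60 = 6, so about 2 to 6 patients. If all of them were stopped under one reading and none under the other, the proportion would differ by 2/60 = 3.3 to 6/60 = 10 percentage points. That is an upper bound, since some would stop for other reasons anyway.

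**The case against.** The strongest reply is that the three statements form a sequence. The row covers a first fall from the starting dose; the next paragraph covers later interruptions; the last paragraph covers Hb below 8 g/dL after a reduction. On that reading the last and most specific statement governs this patient. It also fits the listing of severe persistent anemia among the events requiring olaparib to be discontinued (Sections 3.9 and 6.8). This is plausible, but the protocol does not state the order, does not limit the row to a first event and puts no lower Hb limit on the step-down rule. Even with the sequence accepted, which reduction counts and how far the proviso reaches remain open.

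A second reply is that the proviso separates the cases: step down if another cause is found, stop if none is. That may be the intent, but the step-down paragraph carries no such condition, so both rules still apply when no cause is found.

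Three stronger readings are tempting and are not supported.

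- *The protocol tells sites to resume at an unchanged dose.* No sentence says so. The row speaks of a reduction, which presupposes a higher current dose. The unchanged dose appears only when the row is applied literally at 150 mg bd.
- *The row allows an unlimited hold because it omits the 3-week maximum.* Section 6.8 says of any held drug, "The time a given drug is held should not exceed 3 weeks", and Section 6.8.1.3 addresses failure to recover within 3 weeks. Silence in one row is not a contradiction.
- *TDT shifts by 1.7 points per patient.* TDT is summarized by Kaplan-Meier median and landmark proportions, so 1/60 does not describe its movement. Treatment also stops at progression, and the plan expects 80% PFS events by the analysis. For many patients the rule would change when the TDT event falls, not whether it occurs.

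**Conclusion.** The point holds as one overlap between two explicit rules plus an incomplete table row, all within Section 6.8.1.2. It does not hold as three express contradictory instructions. The overlap concerns a patient at 150 mg bd with an otherwise unexplained Hb below 8 g/dL; the defect in the row also reaches a patient at 100 mg bd.

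The effect is about 1.7 percentage points on the olaparib discontinuation proportion per patient in 60, with further effects on dose intensity, combination exposure and the timing of TDT events. The number of patients affected is unknown. The definition of the primary endpoint, ORR, is not directly affected. The main reasons to act are patient safety and consistent handling across sites. The ambiguity also outlasts the data cut-off, because Sections 4.5 and 9.3 keep the dose modification and stopping criteria in force for patients treated beyond the final protocol visit.

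**What to change.** Reconcile the Table 10 row for Hb below 8 g/dL with the two paragraphs that follow it:

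- set out the olaparib action by current dose level and by first versus later event, so that each case has one instruction and none conflicts with the ban on re-escalation;
- define *the dose reduction* in the stop rule: first or second step, and whether a reduction made for another toxicity or for renal function counts;
- state whether the condition about no other explanation applies to both triggers or only to transfusion.

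Which rule applies is for the sponsor's medical team; this review takes no position on it. The cost is a wording change to one table row and two paragraphs, issued as a protocol clarification. It needs no new data, patients or analyses.

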6.8.1.3 Management of prolonged hematological toxicities while on study treatment

If a patient develops prolonged hematological toxicity such as:

- \geq 2 week interruption/delay in olaparib due to CTCAE Grade 3 or worse anemia and/or development of blood transfusion dependence
- \geq 2 week interruption/delay in 1 or both IPs due to CTCAE Grade \geq 3 neutropenia (ANC <1 x 10⁹/L)
- \geq 2 week interruption/delay in 1 or both IPs due to CTCAE Grade \geq 3 thrombocytopenia and/or development of platelet transfusion dependence (Platelets <50 x 10⁹/L)

Check weekly differential blood counts including reticulocytes and peripheral blood smear. If any blood parameters remain clinically abnormal after 3 weeks of dose interruption, the patient should be referred to hematologist for further investigations. Bone marrow analysis

and/or blood cytogenetic analysis should be considered at this stage according to standard hematological practice. Both IPs should be discontinued if blood counts do not recover to CTCAE Grade ≤ 1 within 3 weeks of dose interruption.

Development of a confirmed myelodysplastic syndrome (MDS) or other clonal blood disorder should be reported as an SAE and full reports must be provided by the investigator to AstraZeneca Patient Safety. Olaparib treatment should be discontinued if patient's diagnosis of MDS and/or acute myeloid leukemia (AML) is confirmed.

6.8.2 Non-hematologic toxicity

Cediranib should be discontinued should any of the following AEs occur: GI perforation; arterial thromboembolic events; PRES (radiologically confirmed); severe or medically significant hemorrhage and severe persistent hypertension despite maximal anti-hypertensive treatment.

Dose modifications for other non-hematologic events on IPs should be managed according to Table 11.

Table 11 General Management of Non-Hematologic Toxicity

Observation	Action
AE resolves promptly with supportive care	Maintain dose level
Any \geq Grade 3 non-hematologic (excluding grade 3 fatigue or easily correctable asymptomatic grade 3 laboratory abnormalities)	Hold IP(s) ^a for up to 3 weeks until toxicity resolves to \leq Grade 1. Treatment may be restarted at one dose level lower for the IP(s) causing the toxicity (see Table 7 and Table 8), at the treating investigator's discretion ^b . Reoccurrence of Grade 3 or 4 toxicity would require dose reduction of both IPs.
Any grade 2 non-hematologic AE or grade 3 fatigue related to cediranib or olaparib that persists despite maximal support.	Hold IP(s) ^a for up to 3 weeks until toxicity resolves to Grade ≥ 1 . Treatment may be restarted at one dose level lower for the IP(s) causing the toxicity (see Table 7 and Table 8), at the treating investigator's discretion ^b .
Grade 3 or 4 non-hematologic AE related to cediranib and olaparib combination that does not resolve to Grade 0-2 within 3 weeks despite maximum supportive care after treating patient at the lowest reduced dose level ^c	Discontinue IP(s)

a. At the discretion of the investigator, one IP may be held or dose modified or discontinued independently if the observed toxicity is attributed to only one of the drugs, while the patient continued to receive the second drug not associated with the observed toxicity. The time a given drug is held should not exceed 3 weeks.

- b. Patients who are at the lowest reduced dose level may have their drug resumed at that dose level after discussion with the AstraZeneca Study Physician and the Principal Investigator if evidence of clinical benefit.
- c. For venous thromboembolic events, treatment may be resumed at the discretion of the investigator once patient is asymptomatic (Section 6.7.3.11).

Abbreviations: AE adverse event; IP investigational product(s)

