6.8.3 Management of cediranib-related toxicity

6.8.3.1 Hypertension

Only doses of cediranib will be modified for hypertension; olaparib doses will not be reduced unless other toxicities are experienced.

In clinical trials, increases in BP have been reported within a few hours of starting cediranib. Since rapid changes in blood pressure can occur with cediranib treatment, with the potential for life-threatening complications if hypertension is not appropriately managed, all patients should check their BP twice daily for at least the first 8 weeks after starting cediranib, or, if antihypertensive management is required, until a stable anti-hypertensive regimen has been established, even if this requires more than 8 weeks. After 8 weeks or once a stable regimen has been achieved, BP monitoring may be reduced to once daily. Twice daily monitoring should be re-implemented after any cediranib dose interruption for 2 weeks or until the patient is re-established on a stable antihypertensive regimen, whichever takes longer.

Patient BP will also be measured during routine study visits: weekly during the first 4 weeks, every 2 weeks during the next 4 weeks and every 4 weeks thereafter, to ensure that BP guidelines are being correctly followed. Increase in BP should be treated promptly with standard antihypertensive therapy, ensuring that the maximum recommended dose and number of antihypertensive medicinal products is reached before considering cediranib dose adjustment. See Appendix G for suggested antihypertensive medications by class. Patients may have up to 4 drugs for management of hypertension prior to any dose reduction in cediranib.

If patients require a delay of > 3 weeks for management of hypertension, discontinuation of cediranib or protocol therapy may be considered after discussion with the PI and the AstraZeneca study physician. In case of persistent or severe hypertension, despite the optimal use of antihypertensive medicinal products and cediranib dose reduction, cediranib should be permanently discontinued.

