6.8.3.2 Diarrhea

Diarrhea is often observed with cediranib. Diarrhea usually starts early (within the first 4 weeks of treatment), however, it can occur at any time during treatment. Management of diarrhea should start at the first sign of diarrhea. Loperamide and advice on how to manage diarrhea should be readily available to patients from the start of cediranib treatment so that they can be applied at first episode of diarrhea. Active and early management of diarrhea is recommended even with Grade 1 diarrhea. Management is as shown in Table 13:

Table 13 Management of Diarrhea

Toxicity	Management/Modifications
Initial grade 1 or 2 diarrhea	
Patients should start loperamide (per standard practice) and continue to take loperamide until patients are free from diarrhea for at least 12 hours. The dose of loperamide should not exceed 16 mg in a 24-hour period. Patients should also be counselled to start a BRAT diet.
 
If diarrhea persists despite 24 hours of loperamide treatment, withhold cediranib for a maximum of 7 days, continue loperamide, and maintain hydration. Cediranib may be restarted at the same dose once patients have been free from diarrhea for 12 hours.
 
Patients should be instructed to contact their study physician if mild or moderate (NCI CTCAE Grade 1 or 2) diarrhea persists for over 48 hours despite treatment with loperamide and cediranib dose interruption.

Table 13 Management of Diarrhea

Toxicity	Management/Modifications
For either persistent grade 2 diarrhea or grade 3 or 4 diarrhea	Patients with persistent or severe diarrhea (NCI CTCAE Grade 3 or higher) may also require dose reduction or discontinuation of therapy with cediranib, follow guidance in Table 7

Abbreviations: BRAT bananas, rice, applesauce, toast; CTCAE Common Terminology Criteria for Adverse Event; NCI National Cancer Institute.

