6.8.3.4 Proteinuria

Proteinuria is a common adverse reaction reported for cediranib and if this occurs during treatment, it should be managed according to [Table 14](#). For management of suspected cases of nephrotic syndrome, refer Section [5.2.1.4](#).

Table 14 Management of Proteinuria

Proteinuria Value if following by urinalysis	Monitoring	Dose modification
Greater than 2+ AND Creatinine $\leq 1.5x$ ULN	Perform UPC	Continue study drugs at planned dose
Greater than 2+ AND Creatinine $> 1.5x$ ULN	Perform UPC	Interrupt cediranib until results of UPC are known (see below)
Based on results of the UPC^a		
UPC ≤ 1.0	Continue monitoring according to Schedule of Assessments (Table 5)	Continue study drugs at planned dose
UPC > 1.0 and ≤ 3.5 AND Creatinine $\leq 1.5x$ ULN	Perform UPC at each routine visit	Continue study drugs at planned dose
UPC > 3.5 OR Creatinine $> 1.5x$ ULN	Perform UPC at each routine visit	Interrupt cediranib for up to 21 days and repeat UPC and creatinine assessment. If UPC resolves to < 3.5 and creatinine to $\leq 1.5x$ ULN, resume cediranib with reduction in cediranib by one dose level. Consider consultation with nephrologist

^a If UPC is < 1.0 and creatinine $> 1.5x$ ULN, AE management should be followed as described above
Abbreviations: ULN upper limit of normal; UPC urine protein:creatinine ratio

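### Table 11 makes reduction of both drugs mandatory when a grade 3 or 4 non-hematologic toxicity recurs, which conflicts with attribution-based rules elsewhere, and no order of precedence is stated

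*Protocol*

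**What the plan says.** Section 6.8.2 sends non-hematologic events to Table 11, apart from a short list that calls for stopping cediranib. In the row for grade 3 or higher events, the first occurrence is handled by cause: "Treatment may be restarted at one dose level lower for the IP(s) causing the toxicity". The same cell then adds: "Reoccurrence of Grade 3 or 4 toxicity would require dose reduction of both IPs". Footnote a, whose marker is on the instruction to hold treatment in that cell, says that "one IP may be held or dose modified or discontinued independently if the observed toxicity is attributed to only one of the drugs".

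Other passages bear on the same decision:

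- Section 6.8, at the investigator's discretion: "the study drugs may be held or dose modified independently if the observed toxicity is attributed to only one of the drugs". This is not limited to a first occurrence.
- Section 6.8.3.1 on hypertension: "Only doses of cediranib will be modified for hypertension; olaparib doses will not be reduced unless other toxicities are experienced".
- Table 13 on diarrhea: "Patients with persistent or severe diarrhea (NCI CTCAE Grade 3 or higher) may also require dose reduction or discontinuation of therapy with cediranib". Olaparib is not mentioned.
- Table 14 on proteinuria, after an interruption: "resume cediranib with reduction in cediranib by one dose level". Olaparib is not mentioned.
- Section 6.8 on reversibility: "Once dose of study drug(s) have been reduced, no dose re-escalation is permitted".

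**The concern.** A rule worded as a requirement stands beside rules that make the choice of drug depend on attribution. For hypertension it stands beside a categorical statement that olaparib is left alone. Section 6.8 points the reader to 6.8.3 and 6.8.4 for some adverse events but does not say that those sections displace Table 11.

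At stake is consistent dosing across about 40 sites, and what the exposure outputs mean. The SAP measures RDI for each drug against 200 mg twice daily and 30 mg once daily (3.3.2). It summarises dose reductions and time at each dose level (4.2.6), and adverse events leading to dose reduction (4.2.9). If sites follow different passages, part of the variation in these outputs reflects the passage used and not the patients' tolerance.

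**Working it through.** The plan gives no figure to reproduce. The check compares the texts and then works out the dose ratios.

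**Step 1: apply each passage to the same event.**

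| Recurrent event | Table 11 recurrence sentence | Other passages |
|---|---|---|
| Grade 3 hypertension | Reduce both drugs | 6.8.3.1: modify cediranib only, olaparib not reduced |
| Grade 3 vomiting attributed to olaparib alone | Reduce both drugs | 6.8 and footnote a: olaparib may be modified alone; 6.8.4.3 covers vomiting but gives no dose rule |
| Grade 3 diarrhea | Reduce both drugs | Table 13 names cediranib only; silent on recurrence |
| Proteinuria that enters the Table 11 row | Reduce both drugs | Table 14 names cediranib only; silent on recurrence |

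The first line is a direct contradiction: both instructions cannot be followed for one patient. In the second, a requirement meets a discretion and no exception links them. The last two are weaker, because Tables 13 and 14 do not say what happens to olaparib on a second episode.

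**Step 2: look for a rule that settles it.** Section 6.8.2 removes from Table 11 only the events that call for stopping cediranib. Among these is severe hypertension that persists despite maximal treatment. Other recurrent grade 3 hypertension is not removed. Section 6.8 refers to the specific sections without ranking them. The hematologic counterpart, Table 9, allows one or both drugs to be reduced on a repeat event, so the protocol does use flexible wording where it intends it.

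**Step 3: size per patient.** Inputs are the dose levels in protocol Tables 7 and 8.

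- Olaparib: 150/200 = 75% at level 1; 100/200 = 50% at level 2.
- Cediranib: 20/30 = 66.7% at level 1; 15/30 = 50% at level 2.

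Let f be the share of treatment time already completed at full dose when the drug not held responsible is cut by one step. Ignoring interruptions and further reductions, its RDI is:

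- olaparib: 100 × [f + 0.75(1 − f)] = 100 − 25(1 − f)
- cediranib: 100 × [f + 0.667(1 − f)] = 100 − 33.3(1 − f)

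The f values here are illustrative, since the documents do not give the timing of recurrence. At f = 0.5 the loss is 25 × 0.5 = 12.5 points for olaparib and 33.3 × 0.5 = 16.7 points for cediranib. The limits are 0 points (f near 1) and 25 or 33.3 points (f near 0). Under the attribution-based passages the loss from this source is 0.

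**Step 4: number of patients.** This needs the probability of a second grade 3 or 4 event attributed to one drug. The documents do not give it, so no count is computed.

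**The case against.** The best defence has three parts.

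1. **Table 11 is the general table, and the specific sections naturally prevail.** This is a sensible reading, and a site would probably not cut olaparib for hypertension against the plain sentence in 6.8.3.1. But the protocol leaves it to inference, and it does not help where the specific section has no dose rule, as with vomiting.
2. **Footnote a supplies the exception.** Its wording covers dose modification as well as holding, so it would be wrong to say that Table 11 ignores attribution. But its marker is on the hold instruction, and the recurrence sentence is worded as a requirement. The footnote makes the table ambiguous within itself and does not settle the question.
3. **The sentence may be a deliberate escalation:** the responsible drug first, both drugs on recurrence. That is possible. The hypertension statement would then need a matching exception, so reconciliation is needed either way.

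Stronger readings are tempting but not supported. A reader might apply the grade 3 or 4 rates in 1.1.4.3 (hypertension 41%, fatigue 27%, diarrhea 23%) to 60 patients and call the result the number affected. Those are rates of any occurrence, not recurrence, from a platinum-sensitive study that used olaparib capsules. Hypertension and diarrhea have their own management in Tables 12 and 13, and Table 12 allows cediranib to resume at the prior dose in some cases. The Table 11 row expressly leaves out grade 3 fatigue. A reader might also infer that reducing the second drug is unjustified. That is a clinical judgement, and the documents do not settle it.

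**Conclusion.** The passages conflict as written and should be reconciled. The conflict is outright for recurrent grade 3 hypertension. It also stands, as a requirement against a discretion, for any recurrent toxicity attributed to one drug. Tables 13 and 14 add context but do not contradict Table 11 on recurrence.

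For an affected patient, one step caps the drug not held responsible at 75% (olaparib) or 66.7% (cediranib) of its starting dose for the remaining treatment, assuming that it was still at the starting dose. The number of such patients is unknown.

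The supported consequence is inconsistent dosing, and with it dose-reduction counts and RDI that depend partly on the passage followed. A reader might go further and infer a distorted objective response rate. The documents give no dose-response information from which to show that, and the SAP's drug-by-drug exposure summaries would show differences in dose, though not which passage led to them.

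**What to change.** Amend the recurrence sentence in Table 11 so that it agrees with footnote a, 6.8 and 6.8.3. The amended text should state two things:

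1. whether the sentence applies when the recurrent toxicity is attributed to only one drug;
2. whether the toxicity-specific sections take precedence over Table 11.

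If reduction of both drugs is intended in every case, 6.8, footnote a and 6.8.3.1 need a matching exception. If it is not, Table 11 does. Which clinical rule applies is for the sponsor to decide.

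The cost is about one sentence in the table and one on precedence, with the usual amendment handling. No procedure, visit, data item or analysis is added.
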